3.6.1 Off-Study Procedure

Authorized staff will notify Central Registration Office (CRO) when a subject is taken off-study. A Participant Status Updates Form from the website (<http://home.ccr.cancer.gov/intra/eligibility/welcome.htm>) main page must be completed and sent via encrypted email to: NCI Central Registration Office [contact].

4 DATA COLLECTION AND EVALUATION

4.1 DATA COLLECTION

All questionnaires will be administered via computer or mobile tablet devices. The PI will be responsible for overseeing entry of data into an in-house password protected electronic system and ensuring data accuracy, consistency and timeliness. The principal investigator, associate investigators/research nurses and/or a contracted data manager will assist with the data management efforts. All data obtained during the conduct of the protocol will be kept in secure network drives or in approved alternative sites that comply with NIH security standards. Primary and final analyzed data will have identifiers so that research data can be attributed to an individual human subject participant.

Adverse events occurring as a result of treatment for the underlying condition or medical treatment for pain will NOT be recorded or reported on this study.

End of study procedures: Data will be stored according to HHS, FDA regulations, and NIH Intramural Records Retention Schedule as applicable.

Loss or destruction of data: Should we become aware that a major breach in our plan to protect subject confidentiality and trial data has occurred, the IRB will be notified.

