5 SAFETY REPORTING REQUIREMENTS/DATA AND SAFETY MONITORING PLAN

5.1 DEFINITIONS

5.1.1 Adverse Event

An adverse event is defined as any reaction, side effect, or untoward event that occurs during the course of the clinical trial associated with the intervention, whether or not the event is considered related to the treatment or clinically significant.

For this study, AEs will primarily include events reported by the patient. Since this is a behavioral intervention and no drug therapy will be administered on this study, physical signs and symptoms as adverse events are not anticipated. A new illness, symptom, sign or clinically significant laboratory abnormality or worsening of a pre-existing condition or abnormality that occurs during the NIH visit which is not directly related to the participation in the baseline treatment sessions or completing the baseline questionnaires will not be reported on this study,

but will be referred to the medical physician responsible for the participant's care. All AEs must be recorded on the AE case report form unless otherwise noted above in Section **4.1**.

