5.2 NIH INTRAMURAL IRB AND CLINICAL DIRECTOR REPORTING

5.2.1 NIH Intramural IRB and NCI CD Expedited Reporting of Adverse Events, Unanticipated Problems, and Deaths

The Protocol PI will report in the NIH Problem Form to the NIH Intramural IRB and NCI Clinical Director:

- All deaths, except deaths due to progressive disease
- All Protocol Deviations
- All Unanticipated Problems
- All non-compliance

Reports must be received within 7 days of PI awareness via iRIS.

5.2.2 NIH Intramural IRB Requirements for PI Reporting of Adverse Events at Continuing Review

The protocol PI will report to the NIH Intramural IRB:

1. A summary of all protocol deviations in a tabular format to include the date the deviation occurred, a brief description of the deviation and any corrective action.
2. A summary of any instances of non-compliance
3. A tabular summary of the following adverse events:
 - All Grade 2 **unexpected** events that are possibly, probably or definitely related to the research;
 - All Grade 3 and 4 events that are possibly, probably or definitely related to the research;
 - All Grade 5 events regardless of attribution;
 - All Serious Events regardless of attribution.

NOTE: Grade 1 events are not required to be reported.

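### Sections 4.1 and 5.1.1 exclude some adverse events by cause, but 5.2.1 and 5.2.2 require deaths and serious events whatever their cause, so the continuing-review safety table would be incomplete

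*Combined protocol and SAP*

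**What the plan says.** Four places in the protocol bear on this.

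- **Section 4.1 (Data Collection)** sets an exclusion by cause that covers both recording and reporting: "Adverse events occurring as a result of treatment for the underlying condition or medical treatment for pain will NOT be recorded or reported". It makes no exception for seriousness or death.
- **Section 5.1.1 (Adverse Event)** repeats that exemption for the form: "All AEs must be recorded on the AE case report form unless otherwise noted above in Section" 4.1. It has a second, narrower exclusion for a new or worsened condition during the NIH visit, which, if "not directly related to the participation in the baseline treatment sessions or completing the baseline questionnaires will not be reported on this study", goes instead to the responsible physician.
- **Section 5.2.2 (continuing review)** requires "A tabular summary of the following adverse events". Two of its rows ignore cause: "All Grade 5 events regardless of attribution" and "All Serious Events regardless of attribution".
- **Section 5.2.1 (expedited reporting)** sends every death to the IRB and the Clinical Director within 7 days, unless it was due to progressive disease.

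Section 5.1.5 counts inpatient hospitalization, or a longer hospital stay, as serious.

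**The concern.** The data-collection rules filter events by cause before they reach the form or the report. The reporting rules ask for serious events and deaths without regard to cause. Staff who follow the first set cannot fully comply with the second.

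What is at stake is the completeness of the safety table that the IRB receives. The cause of an event excluded by 4.1 must also be judged before a form is completed, and the exclusion means that the AE form holds no trace of that judgment. A later reader could not tell an event that was excluded from one that never happened.

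**Working it through.** No figure in the plan is involved, so there is nothing to recompute. The check applies each rule to the kinds of event that could arise.

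| Event | 4.1 and 5.1.1 | 5.2.1 | 5.2.2 | Conflict |
|---|---|---|---|---|
| Non-fatal hospitalization caused by disease or pain treatment | Not recorded, not reported | Not named in the death rule | Required as serious | Yes: recording and reporting |
| Death caused by disease or pain treatment | Not recorded, not reported | Required within 7 days | Required as Grade 5 and serious | Yes: 4.1 against both |
| Serious illness during the NIH visit, not caused by such treatment and not directly related to the sessions or questionnaires | Recordable, not reported | Required only if a death not due to progressive disease | Required as serious | Yes: reporting only |
| Serious event caused by the disease itself, outside the NIH visit | Recorded | Required only if a death not due to progressive disease | Required as serious | No |
| Research-related Grade 3 or 4 event not caused by disease or pain treatment | Recorded | Not named in the death rule | Required | No |

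Three points follow.

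1. **The two exclusions work differently.** Section 4.1 stops recording, so its events are missing at source. The NIH-visit sentence in 5.1.1 stops reporting only. The same section still requires all AEs on the form apart from those exempted by 4.1, so NIH-visit events could be on file and yet be kept out of the table.
2. **The main gap is the first row.** The second row is partly rescued, because the IRB would learn of such a death through 5.2.1. But sending that report breaches 4.1 as written.
3. **The affected events can occur on study.** Section 2.1.2.3 lets patients be considered for entry after one year on a disease treatment that may affect pain. Section 3.6 removes those who start a new treatment likely to affect pain, or whose increased pain requires a new pain treatment or procedure. Participants on continuing treatment stay in. The calendar in Section 3.4 shows AE collection from baseline through Week 40.

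No section states an order of precedence between 4.1 and 5.2.

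**The case against.** The strongest reply is that 5.1.1 defines an adverse event as something associated with the intervention, so a drug side effect was never an AE here and 5.2.2 does not reach it. This does not stand. The same definition goes on to say that relatedness to treatment is not a condition. Section 4.1 itself calls the excluded events adverse events. On that reading, the words in 5.2.2 that set attribution aside would have little work to do.

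Other parts of the defense do stand and limit the point:

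- **The class is narrowed.** Section 2.1.1.7 bars entry when major pain-treatment changes are expected, 2.1.2.3 imposes the one-year wait, and 3.6 removes many who change treatment. Section 7.4 describes a minimal-risk behavioral study.
- **Some information is collected elsewhere.** The Life Events Checklist (Appendix L) asks about hospitalization, days and reason. The 6-month Pain Management Inventory (Appendix N) asks about new NF1 treatments. These self-reports have no grade, seriousness or attribution field, so they supplement the AE form but cannot replace it.
- **Unblinded attribution is not itself a fault.** Trainers and participants cannot be masked in a wait-list trial of in-person therapy, and judging cause is routine. The weakness is only that the judgment behind a 4.1 exclusion is not kept on the AE form.

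A reader might also infer that the trial loses its ability to compare serious events between arms. Sections 1.1 and 6.1 set no such objective and plan no such analysis.

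**Conclusion.** The contradiction is in the current text and the passages must be reconciled. Followed literally, 4.1 leaves the 5.2.2 table without serious events caused by treatment of the disease or of pain, and 5.1.1 leaves out unrelated serious events during the NIH visit. The gap is mainly in non-fatal events.

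The documents give no event rates, so the size cannot be stated; it may be small. The primary endpoint, sample size and efficacy analyses are untouched. This should be corrected, but it does not threaten the trial's main conclusion.

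Three stronger readings are tempting but unsupported:

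- **That events of NF1 itself go unrecorded.** Section 4.1 exempts only events caused by treatment of the condition or of pain.
- **That the table cannot be produced at all.** The research-related rows, and serious events from other causes outside the NIH visit, can still be filled.
- **That the excluded class is the leading source of serious events.** Section 1.2.1 mentions medication side effects and difficult surgery, but ranks nothing by seriousness.

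The conclusion assumes that staff apply 4.1 as written. If they already record serious events despite it, the table may be complete in practice, but the protocol would still contradict itself.

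**What to change.** Make both exclusions subject to 5.2.1 and 5.2.2:

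- **Section 4.1:** add a clause limiting the recording and reporting exclusion to non-serious events. Serious events and deaths then go on the AE form, with an attribution field, and are reported as 5.2.1 and 5.2.2 require. The recording sentence in 5.1.1 defers to 4.1, so it follows without further change.
- **Section 5.1.1:** add a clause limiting the NIH-visit reporting exclusion in the same way. Referral to the responsible physician is unaffected.

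The carve-outs keep their purpose of sparing the team paperwork on non-serious events. The cost is one clause in each section and a few extra AE forms. No study procedure, endpoint or analysis changes.

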5 SAFETY REPORTING REQUIREMENTS/DATA AND SAFETY MONITORING PLAN

5.1 DEFINITIONS

5.1.1 Adverse Event

An adverse event is defined as any reaction, side effect, or untoward event that occurs during the course of the clinical trial associated with the intervention, whether or not the event is considered related to the treatment or clinically significant.

For this study, AEs will primarily include events reported by the patient. Since this is a behavioral intervention and no drug therapy will be administered on this study, physical signs and symptoms as adverse events are not anticipated. A new illness, symptom, sign or clinically significant laboratory abnormality or worsening of a pre-existing condition or abnormality that occurs during the NIH visit which is not directly related to the participation in the baseline treatment sessions or completing the baseline questionnaires will not be reported on this study,

but will be referred to the medical physician responsible for the participant's care. All AEs must be recorded on the AE case report form unless otherwise noted above in Section **4.1**.

5.1.2 Suspected adverse reaction

Suspected adverse reaction means any adverse event for which there is a reasonable possibility that study participation caused the adverse event. For the purposes of safety reporting, 'reasonable possibility' means there is evidence to suggest a causal relationship between study participation and the adverse event. A suspected adverse reaction implies a lesser degree of certainty about causality than adverse reaction, which means any adverse event caused by study participation.

5.1.3 Unexpected adverse reaction

An adverse event or suspected adverse reaction is considered "unexpected" if it is not listed in the protocol or is not listed at the specificity or severity that has been observed. "Unexpected", also refers to adverse events or suspected adverse reactions that are mentioned in the protocol or consent but not at the severity or frequency indicated.

5.1.4 Serious

An Unanticipated Problem or Protocol Deviation is serious if it meets the definition of a Serious Adverse Event or if it compromises the safety, welfare or rights of subjects or others.

5.1.5 Serious Adverse Event

An adverse event or suspected adverse reaction is considered serious if in the view of the investigator or the sponsor, it results in any of the following:

- Death,
- A life-threatening adverse experience
- Inpatient hospitalization or prolongation of existing hospitalization
- Persistent or significant incapacity or substantial disruption of the ability to conduct normal life functions
- A congenital anomaly/birth defect.
- Important medical events that may not result in death, be life-threatening, or require hospitalization may be considered a serious adverse drug experience when, based upon appropriate medical judgment, they may jeopardize the patient or subject and may require medical or surgical intervention to prevent one of the outcomes listed in this definition.

5.1.6 Disability

A substantial disruption of a person's ability to conduct normal life functions.

5.1.7 Protocol Deviation (NIH Definition)

Any change, divergence, or departure from the IRB-approved research protocol.

5.1.8 Non-compliance (NIH Definition)

The failure to comply with applicable NIH Human Research Protections Program (HRPP) policies, IRB requirements, or regulatory requirements for the protection of human research subjects.

Abbreviated Title: ACT Therapy for NF1Related Pain
Version Date: 02/19/2019

5.1.9 Unanticipated Problem

Any incident, experience, or outcome that:

- Is unexpected in terms of nature, severity, or frequency in relation to
 - (a) the research risks that are described in the IRB-approved research protocol and informed consent document; Investigator's Brochure or other study documents, and
 - (b) the characteristics of the subject population being studied; **AND**
- Is related or possibly related to participation in the research; **AND**
- Suggests that the research places subjects or others at a *greater risk of harm* (including physical, psychological, economic, or social harm) than was previously known or recognized.

5.2 NIH INTRAMURAL IRB AND CLINICAL DIRECTOR REPORTING

5.2.1 NIH Intramural IRB and NCI CD Expedited Reporting of Adverse Events, Unanticipated Problems, and Deaths

The Protocol PI will report in the NIH Problem Form to the NIH Intramural IRB and NCI Clinical Director:

- All deaths, except deaths due to progressive disease
- All Protocol Deviations
- All Unanticipated Problems
- All non-compliance

Reports must be received within 7 days of PI awareness via iRIS.

5.2.2 NIH Intramural IRB Requirements for PI Reporting of Adverse Events at Continuing Review

The protocol PI will report to the NIH Intramural IRB:

1. A summary of all protocol deviations in a tabular format to include the date the deviation occurred, a brief description of the deviation and any corrective action.
2. A summary of any instances of non-compliance
3. A tabular summary of the following adverse events:
 - All Grade 2 **unexpected** events that are possibly, probably or definitely related to the research;
 - All Grade 3 and 4 events that are possibly, probably or definitely related to the research;
 - All Grade 5 events regardless of attribution;
 - All Serious Events regardless of attribution.

NOTE: Grade 1 events are not required to be reported.

5.3 DATA AND SAFETY MONITORING PLAN

5.3.1 Principal Investigator/Research Team

The clinical research team will meet on a regular basis to ensure that treatment implementation and follow up data collection are organized and completed in a timely fashion. The principal investigator or AI will review all data within one week of submission. Adverse events will be reported as required above. Any safety concerns, new information that might affect either the ethical and or scientific conduct of the trial, or protocol deviations will be immediately reported to the NIH Intramural IRB using iRIS.

The principal investigator will review adverse event and response data on each patient to ensure safety and data accuracy. The principal investigator will personally conduct or supervise the investigation and provide appropriate delegation of responsibilities to other members of the research staff.

6 STATISTICAL SECTION

6.1 PRIMARY AND SECONDARY OUTCOMES

The primary objective of the trial is to compare pain interference mean score changes from baseline to 8 weeks between the ACT intervention group and the WL group. In the pilot study conducted by our group, mean scores on PII self-report went from 2.1 (1.0) to 1.5 (1.1), with paired differences having a mean change of -0.68 and SD=1.3. Based on this preliminary estimated change for the ACT group, and an assumption of no change in the WL group and a corresponding, reduced SD = 0.8, forty-one patients will be needed per group to have 80% power to detect a difference in change score between the two arms of -0.68, using a t-test with significance level of .05 (two-sided). Secondary analyses will be performed to compare between-group changes from baseline to 8 weeks and from baseline to 32 weeks on the following endpoints: disease-related quality of life, pain severity, pain-related anxiety, and depression. Given the wide age range of the study, we will stratify analyses by age (16 – 24 years; 25 – 59 years). Descriptive statistics will be computed on the primary and secondary outcome measures (means, standard deviations, etc.). If there are significant differences between the groups at baseline (for example, with respect to gender or number of patients on pain medication), analysis of covariance (ANCOVA) may be used to control for these differences statistically during follow-up analyses (treating baseline as a covariate). We also will assess for differences between the group randomized to ACT and the WL group on primary and secondary outcomes, particularly comparing primary results from 0 to 8 weeks for ACT vs. 8 to 16 weeks for WL (receiving ACT starting at 8 weeks); if the results are similar (for example, $p>0.30$ approximately), we will combine these groups to report the overall effect of ACT for 8 weeks, and also examine changes from baseline to 8 weeks and 8 to 16 weeks using an appropriate statistical test. Finally, based on a priori hypotheses and prior literature, we will test for indirect effects of acceptance and psychological flexibility with simple mediation model analyses. We will generate 5,000 bootstrapped samples using Preacher and Hayes' (Preacher & Hayes, 2004) INDIRECT macro. Post-treatment scores will be used for these analyses. Additionally, we will examine whether a previous cognitive diagnosis (ADHD or learning disability), reading ability, disease characteristics (stable vs. progressive disease, location of plexiform neurofibroma), or recent life events, relate to changes over time in the primary outcome with an ANOVA, and if so

we may control for these variables in other analyses with an ANCOVA. Finally, we will compare the psychometric properties of the PII and PROMIS Pain Interference Scale by examining internal consistency in the patient sample (computed by Pearson correlations) and the response to change (as described in the primary objective analysis above). Data will be entered into a secure database, then analyzed using SAS statistical software.

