At the completion of each visit or set of follow-up questionnaires, participants in both groups will receive a small amount of money (\$30) to thank them for their time. The 8-week data will be the primary endpoint and analyses will be conducted to determine changes over time in ACT versus WL on the primary outcome measure (pain interference) and various secondary measures (outlined below). Forty-one patients per arm will provide 80% power to test the 0 to 8-week differences in changes from baseline between the two arms.

| | Days 1-2 | Weeks 1-8 | Week 8 | Weeks 8-16 | Week 16 | Week 32 | Week 40 |
|-----|--|--|--|--|--|--|--|
| ACT | 
 Time 1 evaluations In-person ACT sessions | 
 Weekly emails Video chat weeks 2,4,6 (home) | 
 Time 2 evaluations (NIH) | 
 Continue ACT practice (home) | | 
 Time 3 questionnaires (home) | |
| WL | 
 Time 1 evaluations | | 
 Time 2 evaluations In-person ACT sessions | 
 Weekly emails Video chat weeks 2,4,6 (home) | 
 Time 3 evaluations (NIH) | 
 Continue ACT practice (home) | 
 Time 4 questionnaires (home) |

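### The 80% power depends on an unsourced wait-list SD of 0.8: the planned t-test has about 65% to 80% power for SDs of 1.3 to 0.8, and a prespecified baseline-adjusted test does better with the same 41 per arm

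*Combined protocol and SAP*

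**What the plan says.** Section 6.1 takes its treatment-arm inputs from the group's pilot study. The pilot PII scores had a mean of 2.1 (SD 1.0) before treatment and 1.5 (SD 1.1) after it, and the within-patient change is reported as "paired differences having a mean change of -0.68 and SD=1.3". For the control arm the section makes "an assumption of no change in the WL group and a corresponding, reduced SD = 0.8". The sample size drawn from these inputs is stated as follows: "forty-one patients will be needed per group to have 80% power". The target is a gap of 0.68 points in mean change between the arms, and the planned test is a two-sided t-test at the 0.05 level. Section 1.2.4 repeats the claim without a condition: "Forty-one patients per arm will provide 80% power". The Précis also gives 41 per group at .80 power. None of the three places gives a sensitivity range.

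Section 1.2.2.6 describes the pilot: twelve adolescents in a two-day workshop, ten of them with three-month data, and no control group mentioned. Section 6.1 also mentions ANCOVA with baseline as a covariate, but only as an option if the groups turn out to differ significantly at baseline. It is neither the planned primary test nor the basis of the sample size.

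**The concern.** The sentence presents the smaller SD as a consequence of the zero mean change, and it is not one. A group whose mean stays put can still have widely scattered individual changes. The SD of change is set by the two score SDs and the correlation between them.

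The 0.8 therefore needs its own justification, and the document gives no data, citation or derivation. The input matters because it lowers the planning SD from 1.3 to about 1.08, and the stated 80% rests on that reduction. If the wait-list scores vary more than assumed, a null result would be read as coming from an adequately powered phase III trial when the chance of missing a true effect of 0.68 could be as high as 35%.

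**Working it through.** **Inputs.** All are from section 6.1 unless noted: difference 0.68; ACT change SD 1.3; wait-list change SD 0.8; 41 per arm; two-sided 0.05; pilot score SDs 1.0 at baseline and 1.1 at follow-up. The pilot is taken to have 10 pairs (section 1.2.2.6).

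**1. Reproducing the plan.** The planning SD is sqrt((1.3² + 0.8²)/2) = 1.079. The standard error of the difference is sqrt((1.69 + 0.64)/41) = 0.238, so the noncentrality is 0.68/0.238 = 2.85 on 80 degrees of freedom. The noncentral t gives 80.5% power, and 41 is the smallest number per arm that reaches 80%. The plan's arithmetic is correct.

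**2. Varying only the wait-list SD** (change-score t-test, difference 0.68):

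| Wait-list SD | Power at 41 per arm | Needed per arm for 80% |
|---|---|---|
| 0.8 | 80% | 41 |
| 0.9 | 78% | 44 |
| 1.0 | 75% | 47 |
| 1.1 | 71% | 51 |
| 1.2 | 68% | 55 |
| 1.3 | 65% | 59 |

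If all 90 patients allowed by section 6.2 were analysed (45 per arm), power with SD 1.3 in both arms would be 69%.

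**3. What the pilot says about 0.8.**

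- If the three pilot SDs come from the same patients, r = (1.0² + 1.1² − 1.3²)/(2 × 1.0 × 1.1) = 0.24.
- A change SD of 0.8 needs r = (1.0² + 1.0² − 0.64)/2 = 0.68 with score SDs of 1.0 and 1.0, or (1.0² + 1.1² − 0.64)/2.2 = 0.71 with 1.0 and 1.1.
- With 10 pairs, the Fisher 95% interval for r is about −0.46 to 0.75, which includes both values.
- An untreated change SD of 0.8 can also generate the pilot figures exactly. Start from untreated scores with SD 1.0 at both visits and r = 0.68. Add a treatment response with variance 1.05 and covariance −0.42 with the score at each visit, a correlation of −0.42/sqrt(1.05) = −0.41, so that patients with higher scores gain more. The follow-up variance is then 1 + 1.05 − 0.84 = 1.21 (SD 1.1). The change variance is 0.64 + 1.05 = 1.69 (SD 1.3), and the pre-post correlation is (0.68 − 0.42)/1.1 = 0.24.

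**4. Baseline-adjusted test.** For ANCOVA of week-8 PII with the same follow-up SD and correlation in both arms, the residual SD is the follow-up SD × sqrt(1 − r²). At 1.1 and 0.24 this is 1.07. Power at 41 per arm:

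| Follow-up SD | r | Power |
|---|---|---|
| 1.1 | 0 | 79% |
| 1.1 | 0.24 | 81% |
| 1.1 | 0.5 | 89% |
| 1.2 | 0.24 | 74% |
| 1.3 | 0.24 | 67% |

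**5. Both tests on the same data, by simulation** (41 per arm, normal scores, baseline SD 1.0, difference 0.68). With the pilot SDs and correlation in both arms, ANCOVA has about 81% power against about 65% for the t-test. Under the plan's own assumption (ACT as in the pilot; wait-list change SD 0.8 from score SDs of 1.0 and r = 0.68), it has about 89% against 80%.

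**The case against.** A reader might infer that the pilot contradicts 0.8 and that true power is 65%. The argument would run as follows. The pilot correlation is far below what 0.8 requires. If the extra ACT variance (1.69 − 0.64 = 1.05) were response to treatment independent of the untreated score, the pilot follow-up SD would have been sqrt(1 + 1.05) = 1.43 rather than 1.1.

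The documents do not support that reading. All pilot patients were treated, so the 1.3 mixes natural fluctuation with varying response. The independence assumption carries the argument, and the construction in step 3 shows that dropping it reconciles 0.8 with every pilot figure. With 10 pairs, the 95% interval for the pilot change SD itself (0.89 to 2.37) lies above 0.8, but it describes treated patients. Section 6.1 also does not say that the score SDs and the paired SD come from the same patients. If they do not, the 0.24 cannot be computed this way.

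Some design features favour a smaller SD than in the pilot. The interval is 8 weeks rather than three months. Section 2.1.1.7 excludes anticipated major changes in pain treatment, and section 3.6 removes patients who start a treatment likely to affect pain. The PII entry threshold narrows the baseline spread. As an illustration, truncating a normal baseline (mean 2.1, SD 1.0) at 2.0 and keeping the pilot slope and residual SD gives a change SD of about 1.16 in both arms and 74% power. These points make a value below 1.3 plausible, but the plan does not use them to justify 0.8.

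It is also fair to object that 81% for ANCOVA rests on an unverified wait-list follow-up SD of 1.1. That stands, and the restated power should show the dependence.

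**Conclusion.** The point holds as a gap in justification, not as proof that the trial is underpowered. The stated 80% is conditional on a wait-list SD with no source. The supportable statement for the planned t-test is about 65% to 80% power at 41 per arm, for a wait-list SD between 1.3 and 0.8. The 65% is the equal-SD end of that range, not an estimate of the true power.

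The case for ANCOVA does not depend on settling the 0.8, because it had more power than the change-score t-test under both scenarios simulated. Its 81% assumes a follow-up SD of 1.1 in both arms, a correlation of 0.24 and a true difference of 0.68. The follow-up SD matters more than the correlation within the values shown. The rounded pilot means differ by 0.6. Rounding can reconcile this with 0.68, but at a true difference of 0.6 power would be about 71% with ANCOVA and 70% with the planned test and SDs.

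**What to change.** In section 6.1, before outcome data are analysed by arm:

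- Name ANCOVA of week-8 PII on arm, adjusted for baseline PII, as the prespecified primary test. It replaces both the change-score t-test and the rule that makes baseline adjustment optional after significant baseline differences.
- Restate power on that test, for example: with 41 per arm and a difference of 0.68, power is about 81% if the follow-up SD is 1.1 in both arms and the baseline to week-8 correlation is 0.24 (79% at a correlation of 0, 89% at 0.5; about 74% if the follow-up SD is 1.2 and 67% if it is 1.3).
- Give the unadjusted t-test's power as 65% to 80% for a wait-list change SD of 1.3 to 0.8, and either cite a source for 0.8 or label it an assumption.
- Bring the power statements in the Précis and section 1.2.4 into line.

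The sample size, visits and data collection do not change. The cost is a change of primary test, which is more than a wording edit, and a less favourable stated figure for the unadjusted test.
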